5.9 Concomitant medications

All concomitant medication should be recorded and verbally confirmed with the subject during visit S1. Any change in medication (i.e. addition or discontinuation of a medication and any change in dose or frequency) should be recorded during all study visits. Specific attention should be given to pain medications and the following data should be recorded: pain medications prescribed specifically for wound pain versus pain medications written for non-ulcer related pain. For each pain medications specific dose should be listed in visit S1. For PRN pain medications the specific number of pills taken weekly should be estimated with the subject in every visit.

5.10 Study ulcer history

Specific history of Study Ulcer should be documented and the following data recorded:

- a. Study ulcer duration. This will be defined as time lapsed since the last time the skin at the ulcer site was completely epithelialized without drainage or a scab.
- b. Study ulcer location: Right versus left leg and specific location on the leg: proximal calf OR distal gaiter area, malleolus AND anterior, posterior, lateral OR medial.
- c. Non study ulcer number and locations as above as well as shortest distance from Study Ulcer when on the same limb.
- d. Current Study Ulcer treatment including cleaning methods, primary and secondary dressing and compression therapy.
- e. Study ulcer treatments in the 30 days before visit S1 (record as above)
- f. Any other previous Study Ulcer treatments.
- g. Age at first VLU ever.
- h. Total number of VLU ever.
- i. History of VLU recurrence defined as opening of the skin with visible ulcer, drainage or scab in a location of a wound that was previously 100% epithelialized without drainage or scab.
- j. History of deep vein thrombosis.
- k. Specific history of lipodermatosclerosis, leg dermatitis, itch, edema, varicosities, edema etc.
- l. Specific history of any surgical treatment for venous reflux such as sclerotherapy, vein stripping, vein ablation etc. on any limb.

5.11 Vital signs

At every study visit the following vital sign will be assessed: temperature (in Celsius), blood pressure (mmHg), heart rate (beats per minute), respiratory rate (breaths per minute), weight (kilograms), pain (VAS see assessment separately), peri-wound itch (Numeric Rating Scale (NRS), see appendix D), overall body itch (NRS, see appendix D).

5.12 Pain assessment

Pain is a stated outcome in this study. The intensity of pain at the study ulcer is to be assessed at every visit using VAS. The Visual Analog Scale is a validated pain assessment tool.[25] It is critical that pain assessment be conducted prior to removal of any dressing or compression system and prior to any physical manipulation of the limb. Pain assessments are conducted in all phases of the study as detailed in the schedule of assessments.

The VAS scale is 100 mm in length and only original copies placed in the subjects' source docs a priori are to be used. Photocopy of the scale may jeopardize measurements and later data analyses and therefore only the originals should be used. The scale marks the words "no pain" by the left end of the horizontal bar and "The worst pain I can imagine" by the right end of the bar. At each assessment the subject is asked to mark the level of

current pain by marking a notch along the bar. The distance from the left end of the bar to the notch is measured and recorded at each assessment.

For analysis and interpretation the following categories will be used:

- 0 - <5 mm - no pain
- 5 - <45 mm - mild pain
- 45 - <75 mm - moderate pain
- 75-100 mm - severe pain

5.13 Focused physical exam

The exam will be performed at visits detailed in the table of assessments i.e. the study calendar. Focused exam of the subject's lower extremities will be performed based on the systems described in table 2.

System	Assessment
Vascular	Pulses (femoral, popliteal, dorsalis pedis, tibialis posterior), skin temperature, capillary refill
Neurological	Sensory monofilament testing
Cutaneous	Presence of hyperpigmentation, edema, atrophie blanche, varicosities, scars, dermatitis

Table 2. Focused physical exam

5.14 Wound area measurement

Wound area will be measured at each visit as detailed in the table of assessments. The area is measured in centimeters squared. The area is measured using a ruler and measuring the length of the longest wound axis possible and multiplying by the length of the perpendicular axis.

Additionally, the wound will also be measured using the InSight™ system (eKare Inc.)[26]. Detailed operation instructions are found in appendix E.

FIGURE 1. Wound area measurement

5.15 Product application

5.15.1 Standard care:

During the screening phase and follow up phase Study Device and Comparator are not applied. Instead, only the secondary dressing is used and applied directly to the wound bed. Dressing decision chart is shown in table 3.

5.15.2 Primary dressing:

Dressings are applied at all visits as indicated by the table of assessments. Study dressing is applied per randomization. After wound cleansing, exam, debridement, measurement and photography, wound dressing is applied to the wound. Dressing should cover the entire wound and overlap up to 1 cm beyond wound edges. Dressing should be in contact with wound bed.

5.15.3 Secondary dressing:

The primary dressing is secured in place by a secondary dressing. Choice of secondary dressing will be based on exudate level as detailed in table 3.

Secondary dressing decision chart: [27]

Classification	Description	Per protocol dressing
Dry	Wound bed is dry; there is no visible moisture and the primary dressing is unmarked; dressing may be adherent to wound.	Cutimed Hydro B

Moist	Small amounts of fluid are visible when the dressing is removed; the primary dressing may be lightly marked.	
Wet	Small amounts of fluid are visible when the dressing is removed; the primary dressing is extensively marked, but strikethrough is not occurring;	Cutimed Siltec B
Saturated	Primary dressing is wet and strikethrough is occurring; periwound skin may be macerated	
Leaking	Dressings are saturated and exudate is escaping from primary and secondary dressings onto clothes or beyond;	Cutimed Sorbion

Table 3. Secondary dressing decision chart

Secondary dressing is secured in place by the first layer of the compression system.

5.15.4 Dressing storage:

All study dressing will be stored safely in a locked space. Products will be stored properly and according the manufacturer's storage instructions.

5.16 Tissue collection

Tissue collection will be conducted at visits T0, T2 and T3 as per appendix A. All collection containers are pre-labeled with the subject ID. After collection, the date is written on the container label.

5.17 Sharp debridement

Ulcer debridement is considered standard care. Debridement should be conducted as detailed in the table of assessments. Debridement allows proper wound measurement and assessment. Tissue with eschar, slough or other devitalized tissue will be removed and debridement material collected per appendix A. Sharp debridement will be conducted in this study using a curette, scalpel or other sharp device deemed appropriate by the Investigator.

Careful sharp debridement is to be performed as follows:

1. Study ulcer and the surrounding skin are cleansed with saline.
2. All non-viable tissue is removed from the study ulcer bed and edges using clean technique and avoiding excess debridement.

3. Direct pressure is applied to the wound to achieve hemostasis. Cautery is to be avoided as much as possible and only used if pressure methods failed to achieve hemostasis.

5.18 Compression

Four-layer compression will be standard care for all subjects. The Comprifore® system will be used as described in Appendix B.

5.19 Adverse events

5.19.1 Collecting Adverse Events

Study staff and PI are responsible for soliciting, recording and reporting any adverse event during the study period. In addition to unsolicited reports by subjects, the PI and study staff will open every visit by asking for any change in health or any other complaint since the last visit.

5.19.2 Definition of an adverse event

In this study an adverse event (AE) will be defined based on FDA CFR Title 21: "Adverse event means any untoward medical occurrence associated with the use of a drug in humans, whether or not considered drug related" [28]. Therefore an AE is considered as any unplanned medical occurrence that affects subject's health and/or well-being. The adverse event need not be directly related to the study device or procedure. As such, an adverse event may include any unintended outcome such as a symptom or a new diagnosis or worsening or improvement of existing medical condition.

Serious adverse event (SAE) is defined according to FDA CFR title 21: "Serious adverse event or serious suspected adverse reaction. An adverse event or suspected adverse reaction is considered "serious" if, in the view of either the investigator or sponsor, it results in any of the following outcomes: Death, a life-threatening adverse event, inpatient hospitalization or prolongation of existing hospitalization, a persistent or significant incapacity or substantial disruption of the ability to conduct normal life functions, or a congenital anomaly/birth defect. Important medical events that may not result in death, be life-threatening, or require hospitalization may be considered serious when, based upon appropriate medical judgment, they may jeopardize the patient or subject and may require medical or surgical intervention to prevent one of the outcomes listed in this definition. Examples of such medical events include allergic bronchospasm requiring intensive treatment in an emergency room or at home, blood dyscrasias or convulsions that do not result in inpatient hospitalization, or the development of drug dependency or drug abuse".

A SAE is therefore an AE that:

1. Results in death.
2. Is life-threatening at the time of the AE.
3. Results in an inpatient hospitalization or prolongation of existing hospitalization.
4. Results in a persistent or significant incapacity or substantial disruption of the ability to conduct normal life functions.

5. Is a congenital anomaly/birth defect.
6. May require medical or surgical intervention to prevent one of the outcomes listed above.

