3.2.2 Secondary outcomes

Secondary outcomes will include:

Microbiological outcomes: bacterial silver resistance characterization on molecular and phenotypic level over time (see appendix A for molecular microbiology protocol).

Clinical wound outcomes: healing rate and percent reduction in area over 6 weeks will be calculated by measuring wound area at each visit and dividing the area change by 6 to calculate average wound healing rate in cm^2/week and the average percent reduction for each study arm.

Complete healing at 6 weeks – the proportion of subjects in each study arm in which the study ulcer achieved complete healing at visit F1.

Pain related outcomes: pain assessments will be collected at every visit using visual analog scale (VAS) and time from visit T0 to clinically meaningful decrease in pain (i.e. 33% reduction from baseline) [21] will be calculated. Additionally, time to first indication of no pain will be calculated (i.e. VAS < 5mm)

Quality of life measurements: the EQ-5D-5L [22] and the Wound Quality of Life (WQoL) [23, 24] instruments will be used and assessments take place at visits T0, T4 and F1.

Safety outcomes: adverse events will be recorded at every visit and type and frequency logged and compared between arms.

4. Study population

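### Section 5.19.2 lets unintended improvement of an existing condition count as an adverse event, and no rule keeps such events out of the between-arm safety comparison

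*Combined protocol and SAP*

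**What the plan says.** Section 5.19.2 defines an AE in three steps. It first quotes a federal definition: "Adverse event means any untoward medical occurrence associated with the use of a drug in humans, whether or not considered drug related". It then restates this for the trial: "Therefore an AE is considered as any unplanned medical occurrence that affects subject's health and/or well-being". Finally it gives examples: "an adverse event may include any unintended outcome such as a symptom or a new diagnosis or worsening or improvement of existing medical condition". The words at issue are the last of these, "worsening or improvement of existing medical condition".

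Section 5.19.1 says how events are found: staff "open every visit by asking for any change in health or any other complaint since the last visit". Section 3.2.2 sets the outcome: "adverse events will be recorded at every visit and type and frequency logged and compared between arms". Section 7 gives safety no analysis of its own; secondary endpoints, safety included, are to be handled by methods similar to those for the primary endpoint. Section 5.3.1 states that the PI is not blinded, and Section 5.19.4 makes the PI responsible for the causality of each AE.

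**The concern.** The three steps of the definition do not agree. The cited text needs an untoward event. The restatement needs only an unplanned one, which says nothing about direction. The examples then include improvement outright, which cannot be untoward. A site following the examples would log some benefits as AEs.

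This reaches an outcome that is compared between arms. The opening question at each visit asks about any change, so favourable changes will be mentioned. No rule says when an improvement is to be logged, and none sets it aside at analysis. Section 5.8 lets the PI class a new diagnosis as not an AE, but it says nothing similar about improvements. Under Section 7 a goal of this pilot is to supply effect estimates for planning later studies. AE frequencies that mix benefit with harm would be poor estimates for that purpose.

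**Working it through.** The documents give no expected AE rate, safety margin or safety power, so there is no figure to reproduce. The check is first of the text, then an illustration on assumed rates.

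**Text, side by side**

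| Step | Where | Direction of effect |
|---|---|---|
| Cited definition | 5.19.2 | Harm only (*untoward*) |
| Restatement | 5.19.2 | None (*unplanned*) |
| Examples | 5.19.2 | Both worsening and improvement, if *unintended* |
| Elicitation | 5.19.1 | None (any change in health, or any complaint) |
| Outcome | 3.2.2 | Takes whatever was logged |
| Analysis | 7 | No exclusion or separate table for favourable changes |

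Nothing after the definition restores the requirement that an event be harmful.

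**Illustration**

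Inputs from the documents: 15 completers per arm (Section 4.1) and alpha 0.05 (Section 7; two-sided assumed, since sidedness is not stated). Assumed inputs: *h*, the chance that a subject has a harmful event, and *i*, the chance that a subject has an improvement logged as an AE, taken as independent of each other. Then

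P(at least one AE) = 1 − (1 − *h*)(1 − *i*).

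*Same improvement rate in both arms (dilution).* The difference between arms becomes (1 − *i*)(*h*₁ − *h*₂). With true harm of 40% and 20%, the true difference is 20 points. At *i* = 0.20 it becomes 0.80 × 20 = 16 points, and at *i* = 0.50 it becomes 0.50 × 20 = 10 points. If frequency means events rather than subjects, which Section 3.2.2 leaves open, the expected difference in counts is unchanged, but the added events shrink the ratio and add noise.

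*Different improvement rates, equal harm (bias).* The spurious excess is (1 − *h*)(*i*₁ − *i*₂).
- Central case, *h* = 0.30, *i* = 0.50 and 0.20: 1 − 0.70 × 0.50 = 65% against 1 − 0.70 × 0.80 = 44%, an excess of 21 points, or about 9.8 against 6.6 subjects of 15.
- Smallest case checked, *h* = 0.40, *i* = 0.40 and 0.20: 0.60 × 0.20 = 12 points.
- Largest case checked, *h* = 0.20, *i* differing by 0.30 (50% and 20%, or 60% and 30%): 0.80 × 0.30 = 24 points.

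Exact binomial enumeration at 15 per arm for the central case: the chance that the arm with more improvements shows more subjects with an AE is 0.84, against 0.42 if only harms are counted. Over all cases checked, the chance of a significant Fisher test against that arm is 4% to 14%.

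*Different harm as well.* With true harm of 30% and 40%, and improvements logged in 50% and 20%, the proportions become 1 − 0.70 × 0.50 = 65% and 1 − 0.60 × 0.80 = 52%. The order is reversed.

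With improvements excluded, each proportion returns to *h*, and equal harm gives an expected difference of zero.

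**The case against.** The strongest reply is that the examples sentence, read whole, is narrow. It is permissive (*may include*) and covers only unintended outcomes. Healing of the study ulcer is a stated secondary outcome, so it is intended. Edema reduction is named in Section 2 as central to standard care. Both fall largely outside the sentence. This stands, and it leaves mainly unlooked-for improvement in other conditions, for example dermatitis, itch or an unrelated illness.

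A reader might go further and infer that the definition penalises the more effective dressing. The documents do not support that. All subjects receive the same four-layer compression (Section 5.18), so improvement due to compression should be similar in both arms. The arms differ in the wound contact layer, and nothing in the documents shows that this would change other conditions differently. A bias needs improvement, or its logging, to differ by arm. Unblinded logging without a rule makes that possible but does not establish it.

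Other mitigating points stand in part. Events are logged by type, so an improvement may be visible as one, though no rule requires it to be separated. The serious-event criteria in Section 5.19.2 concern harms or interventions to prevent them, so serious-event reporting is essentially untouched. No AE threshold or stopping boundary depends on the count. Experienced staff may ignore the phrase, but if some do and others do not, the counts are not reproducible.

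**Conclusion.** The point holds as a contradiction within Section 5.19.2 that carries into a compared outcome. As written, unintended improvements in existing conditions other than study-ulcer healing could be counted with harms. The consequence is dilution of the safety comparison, with bias only if improvement or its logging differs between arms.

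The size cannot be derived from the documents. The 12 to 24 points rest wholly on assumed harm rates of 20% to 40%, assumed improvement rates differing by 20 or 30 points, independence, and 15 per arm. They show what the wording permits and do not forecast what will happen. For a pilot without a power calculation this is a minor point, worth making because the repair is so cheap.

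**What to change.** In Section 5.19.2, make two edits:
1. Delete *or improvement* from the examples.
2. Replace *unplanned* with *untoward* in the restated definition.

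The second edit is needed because the deletion alone leaves a restatement that is still neutral on direction. If the sponsor wants improvements captured, add a sentence saying that they are recorded separately and excluded from the AE frequency comparison in Sections 3.2.2 and 7.

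The cost is a few words. No visit, sample, assessment or clinical procedure changes. If subjects have already been enrolled, logged AEs should be checked once for entries that record only an improvement.

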5.19.3 Documenting and reporting adverse events

All adverse events need to be recorded and reported to the local IRB and the sponsor in a timely manner and in accordance to local regulations.

5.19.4 Assessment of advance event causality

For each AE the PI is responsible for assessing the relationship between study procedure including application of study device and the AE in order to determine causality. The relationship of AE to study activities will be recorded in the AE log. The PI will use the following terms to describe relationship of AE to study activities:

Probable: the AE appears to follow a temporal sequence following study related activities, or has a dose relationship with study activities (i.e. worse when activity increased and visa versa) and cannot be attributed to other causes such as past medical history.

Possible: the AE appears to follow a temporal sequence following study related activities, or has a dose relationship with study activities (i.e. worse when activity increased and visa versa) but could be attributed to other causes such as past medical history and other therapies.

Unlikely: the AE does not appears to follow a temporal sequence following study related activities, and does not demonstrate a dose relationship with study activities (i.e. worse when activity increased and visa versa) and could reasonably be attributed to other causes such as past medical history and other therapies.

Cannot assess: the PI cannot make determination of causality at this time due to insufficient information and/or contradictory or unreliable information. The PI will frequently re-evaluate the AE in order to classify it into one of the classes above.

5.20 Fitting for stocking

Once healed, subjects will be fitted with compression stocking (Jobs Softfit) as per the manufacturer's instructions.

5.21 Instructions for follow up care

Once subjects are identified as healed, they will move into the follow up phase. Subjects who completed the treatment phase (regardless of healing status) will be moved to the follow up stage as well. While in the follow up phase, subjects will be returned to the care provider who referred them to the study and follow up care will consist of appropriate compression therapy, wound care (if needed) and other medically indicated treatments as determined by the PI.

5.22 Ankle- brachial – index (ABI)

ABI should be calculated for all subjects during visit S1. The protocol for measuring and calculating ABI is detailed in appendix C. The result of the test should be documented in the CRF.

6. Study conduct

6.1 Schedule of assessments

Assessments will be conducted as described in the protocol according to the schedule presented in Table 1.

6.2 Handling unscheduled visits

At any point during the study subjects may present for an unscheduled visit or may require an unscheduled visit at the discretion of the PI. Common reasons for unscheduled visits may include (but are not limited to): adjustment or reapplication of compression system, dressing overwhelmed with exudate, adverse event.

In the event of an unscheduled visit, the details of the visit will be recorded in the source documents and adverse events logged as needed.

6.3 Handling missed visits

It is preferred that subjects are seen at regular intervals. However, this may not be possible at times. If a subject needs to miss a visit, every effort should be made to reschedule as close as possible to the original date and then resume following visits at the original intervals. For example, if a subject regularly visits on Wednesdays and will miss a visit and a makeup visit is scheduled for that Friday, the next visit should return to the original intervals and be scheduled for the next Wednesday.

6.4 Stopping rule:

The PI may decide to stop the trial due to safety concerns at any time during the trial. The PI may consult the local Institutional Review Board (IRB) and/or Sponsor for safety related decisions.

7 Statistical methods

This study is a single center randomized longitudinal pilot study to investigate the effectiveness of Cutimed® Sorbact® (Study Device) compared to Comparator (silver impregnated contact layer dressing - Acticoat®) in modifying bacterial load in venous leg ulcers (VLU). Efficacy will be measured as the difference in change in bacterial load compared to baseline between two study arms i.e. Study Device vs. Comparator. This study will also

compare bacterial silver resistance based on genetic and phenotypic characterization over time, healing rate, complete healing at 6 weeks, pain, quality of life (QOL) measurements and adverse events as secondary endpoints.

We expect to study n=30 subjects for both the primary and secondary endpoints. The number of subjects estimated for the study (n=30) is not based on hypothesis driven statistical power calculation. Rather, as a pilot study, a goal for this investigation is to generate effect estimates that will assist in determining an appropriate sample size for future studies.

Prior to performing statistical analyses on quantitative study data, the data will be checked, screened and verified to ensure the integrity of the database. Data screening will focus on several aspects. We will determine the amount, the pattern, and randomness of missing data. We will define outliers as observations that appear to be very high or very low, and decide how to proceed based on the presumed cause. We will identify inconsistencies within a single variable and between variables. Initially, we will perform an explanatory data analysis; visually via graphics/plots and numerically by descriptive statistics with mean, standard deviation for measurements taken on a continuous scale, and frequencies and percentages, various types of cross-tabulations for measurements taken on a categorical scale. Corresponding confidence intervals (CI) for means and proportions will be calculated. To have a better understanding of the relationships among different study measurements, parametric or non-parametric correlation coefficients, bivariate/multidimensional cross-tabulations will be constructed. All the descriptive statistics will be reported for all subjects and by study arm.

The primary endpoint of the study, the bacterial load in CFU/g, will be calculated for each wound at visits T0, T2 and T3 among Study Device and Comparator arms. The difference in means of the bacterial load from T3 to T0 will be calculated and compared between study arms with Student's t-test. To be able to study the trajectories of the bacterial load over time, overall and by study arms, the time series plots will be depicted and repeated measures regression analysis will be performed where time and study arm as the main effects. Types of variance-covariance matrix will be determined by standard statistical procedures. We plan to expand the regression model and include other subject characteristics for additional covariate adjustment. Adjusted regression coefficients and corresponding 95% confidence interval (95%CI) will be reported for the study arm as the main effect in the regression models.

The secondary endpoints such as microbiological outcomes, clinical wound outcomes, pain related outcomes, quality of life measurements, and safety outcomes will be analyzed with similar statistical methods as the primary endpoint.

Due to the nature of a pilot study with limited sample size, regression models might have convergence problem i.e. regression estimates and corresponding 95%CI might not be estimable.

Therefore, we might explore different regression models as a secondary source of modeling approach. Regression model assumptions will be checked and model diagnostics will be done based on the appropriate statistical tools. Transformations of the data in order to meet statistical assumptions will be undertaken when indicated. Type-1 error will be set to 5% (alpha=0.05) and will be adjusted for multiple comparisons. Standard model diagnostic tools will be used. All of the statistical analyses will be carried out using SAS (SAS Institute Inc., Cary, NC) or R (R Foundation for Statistical Computing, Vienna, Austria. <http://www.R-project.org/>).

8 Regulatory and ethical issues

8.1 protocol institutional approval

The PI will submit the protocol and all related materials (e.g. ICF) for approval by the local Institutional Review Board (IRB) before any study related activity commences. All local and Federal regulatory rules will be followed and a dedicated regulatory monitor will be assigned to the protocol.

8.2 informed consent

During visit S1 and before any study activities are initiated, each subject will be provided with detailed information about the study and ample time to review ICF in order to obtain an informed consent. The subject (or legally authorized representative) will then be given the opportunity to ask any questions about the study and all questions will be answered. The subject (or legally authorized representative) will then sign and date the ICF according to the regulatory and legal requirements. ICF will be signed, dated and retained by the PI as part of the study records. No study related activities or procedures will take place before valid consent is obtained in an ethical manner and without.

In the case of a protocol amendment, the ICF will be revised to reflect said changes as required by IRB. Once revised, the ICF will be signed by all new subjects enrolled from that date forward as well as for all subjects still in the study (i.e. in the screening, treatment or follow up phase) when they are next scheduled to appear for a study visit.

